Anesthesia for hip fracture surgery can be achieved by either general anesthesia (GA) or spinal anesthesia (SA). The potential advantages of SA include opioid-sparing effects, lessened impacts on the respiratory and gastrointestinal systems, and reduction in rates of adverse outcomes such as pneumonia, mechanical ventilation, intensive care unit (ICU) admission, venous thromboembolism (VTE), myocardial infarction (MI), stroke, transfusion, readmission, and prolonged postoperative length of stay (15, 16). However, a recent randomized control trial found no difference between SA and GA for older adults undergoing hip fracture surgery for the primary outcome of survival and recovery of ambulation at 60 days (17).

While emerging evidence shows COVID-19 infection increases mortality after hip surgery, there is a lack of research examining whether the choice of anesthetic technique modifies the postoperative mortality and morbidity of hip fracture patients with COVID-19 infection. This is particularly important due to the high mortality (35% in COVID-positive patients, vs. 2% in patients without COVID) (12), with the potential for SA to modify this risk by circumventing the need for airway interventions. SA may also offer superiority over general anesthesia for limiting aerosol generation and exposure of operating room staff (18) during the pandemic. While SA may reduce the risk of pulmonary morbidity by reducing the need for airway interventions, its motor block on accessory muscles and the need for sedation may adversely impact ventilation.

In this study, our goal is to evaluate the adjusted association between anesthesia technique and mortality and morbidity after hip fracture surgery for patients who tested positive for COVID-19. Our primary objective is to determine for patients undergoing hip surgery with COVID-19 infection, whether SA, as compared to GA, is associated with a lower rate of mortality 30 days postoperatively. Our secondary objective is to determine whether SA, as compared to GA, is associated with a lower rate of morbidity 30 days postoperatively. To provide context for interpretation, we will describe the epidemiology of the following rates during versus before the 2020 COVID-19 pandemic (January to December 2021, compared to 2017 to 2019): 1) SA versus GA utilization for hip fracture surgery, and 2) mortality and morbidity for hip surgery patients without COVID-19 infection. Finally, we will quantify the mortality and morbidity for patients with versus without COVID-19 infection undergoing hip fracture surgery, stratified by SA and GA.

Methods

Study Design

Approval will be gained from the University of British Columbia Providence Health Care Research Ethics Board. The requirement for written informed consent will be waived for use of deidentified data. Patient information will be obtained for the retrospective cohort analysis using the NSQIP® (general dataset linked with the Hip Fracture Procedure Targeted Dataset), a prospectively-collected multicentre dataset with more than 150 clinical variables within 30 days after surgery (19). The study will be pre-registered prior to data analysis (Clinicaltrials.gov) and reported according to The Strengthening the Reporting of Observational Studies in Epidemiology (STROBE) guidelines.

Setting

The setting of this study will be patient data obtained from the multicentre generated NSQIP Hip Fracture Procedure Targeted Dataset. The period of patient data obtained will include from January 2017 through December 2021. We will omit the data from January 2020 to December 2020 given there was no reporting of COVID status during this period. Data will only be obtained from patients undergoing hip surgery with mortality and morbidity gathered for 30 days postoperatively.

Participants

Inclusion

The study will include all patients 19 years or older who are sampled in the NSQIP Hip Fracture Procedure Targeted Dataset from January 2017 through December 2019 and January to December 2021 undergoing surgical fixation of hip fractures using either general and/or spinal anesthesia. In case of reduced Procedure-Targeted data collection during the COVID-19 pandemic, we will also create a total open hip fracture cohort using relevant *Current Procedural Terminology* codes (27244, 27245, 27269, 27236, or 27248) (20).

Exclusion

Patients with the primary or secondary anesthetic technique listed as local anesthesia alone, local anesthesia with intravenous sedation, epidural, and those with no reported anesthesia technique will be excluded. We will further exclude patients with American Society of Anesthesiologists (ASA) Physical Status (PS) V (defined as “5-Moribund”), and patients with ventilator-dependence preoperatively. Patients with platelet counts $< 80,000/\text{mm}^3$ within 90 days before surgery (21), INR ≥ 1.5 , or PTT > 35 seconds were also excluded for the likelihood of these patients being considered ineligible for SA based on previous guidelines (22, 23).

COVID-19 cohorts

The study will be divided into three cohorts: those undergoing hip surgery 1) without COVID-19 infection January to December 2021, 2) with COVID-19 infection January to December 2021, and 3) pre-pandemic from January 2017 to December 2019.

Due to the variable duration of asymptomatic period that can precede symptoms and diagnosis, COVID-19 infection status will be classified as follows. In our primary analysis, COVID-negative patients will be defined as rows 1 in Table 1, and COVID-positive patients will be defined as row 4. In NSQIP, preoperative COVID status denotes within 14 days before surgery, and patients with preoperative COVID are always coded “No” for postoperative COVID. NSQIP does not have previous history of COVID prior to 14 days, which is a major limitation given the increased mortality of patients with recent COVID undergoing surgery (24).

As patients with postoperative COVID-positive status are difficult to interpret due to variable incubation period and the possibility of COVID-19 contraction while in hospital post-operatively, we will perform sensitivity analysis using alternative definitions for the COVID-positive cohort, including 1) rows 2, 4, and 6 (i.e. laboratory confirmed preoperatively or post-operatively), 2) rows 4 and 6 (i.e. laboratory confirmed or symptomatic preoperatively), and 3) rows 2, 3, 4, 5, and 6 (i.e. suspected and laboratory confirmed anytime preoperatively or post-operatively).

Table 1

Row #	NSQIP classification	
	Preoperative COVID (within 14 days before surgery)	Postoperative COVID
1	No	No
2	No	Yes – lab confirmed
3	No	Yes – suspected
4	Yes – lab confirmed	No
5	Yes – suspected*	No
6	Yes – suspected	Yes – lab confirmed

*Suspected denotes COVID-19 infection suspected by patient preoperative pneumonia or dyspnea

Outcomes

All outcomes (please see Appendix 1 for detailed definitions) will be measured within 30 days postoperatively, with the exception of length of stay (LOS) which was the total number of days from the day of operation to the day of discharge from hospital (19).

Primary outcomes

The primary outcome is all-cause 30-day mortality following hip fracture surgery.

Secondary outcomes

Secondary outcomes are MI, stroke or cerebrovascular accident (CVA), postoperative delirium, pneumonia, acute renal failure, transfusion, being on ventilator postoperatively (>48 hours), being still in hospital >30 days, length of stay (LOS), discharge destination as home versus not home, hospital readmission, and unplanned reoperation. There will be three composite outcomes: 1) venous thromboembolism (VTE), defined as pulmonary embolism or deep venous thrombosis, 2) sepsis, defined as sepsis or septic shock, and 3) any complication listed above or death. The definitions of secondary outcomes collected from NSQIP variables are included in Appendix 1 (Data Extraction Form).

Exposure

The exposure to either SA or GA will be modelled as a binary variable (please see Appendix 1 for detailed definitions). SA will be defined as having either spinal or managed anesthesia care (MAC) documented the primary anesthesia technique, without GA secondary anesthesia technique. In NSQIP, regional anesthesia with MAC would be coded as MAC for the principal technique. Since it is highly unlikely that patients can tolerate hip fracture repair under sedation alone, MAC is counted as SA for the analysis. Those receiving both SA and GA (presumably either failed spinal and/or conversion to GA for other purposes) will be excluded from the primary analysis, but included in *a priori* sensitivity analysis with cohort characteristics displayed as a third comparison group, and analyzed as part of the GA group for the multivariable logistic regression.

Confounders

We selected an *a priori* list of potential confounders to adjust for the choice of anesthetic technique, based on availability within NSQIP, literature, clinical experience, and consensus within our multidisciplinary team. The confounders are: age, sex, race, body mass index (BMI) (calculated from height and weight in NSQIP), American Society of Anesthesiologists (ASA) Physical Status (PS), smoker within one year preoperatively, severe obstructive chronic pulmonary disease (COPD), dyspnea, coagulopathy (bleeding disorders), congestive heart failure (CHF), hypertension on medications, preoperative renal failure (acute renal failure, dialysis, and/or GFR < 60 mL/min/1.73 m² based on preoperative creatinine) (25), diabetes, preoperative functional status, preoperative delirium or dementia, systemic sepsis, total operating time, and days from hospital admission to operation. The definitions of potential confounding variables collected from NSQIP variables are included in Appendix 1 (Data Extraction Form). Since some of the potential confounders may provide similar information, collinearity will be assessed and variables will be combined or eliminated as described in the statistical analysis plan below.

We acknowledge that NSQIP is missing several important confounders, particularly in terms of having little clinical information indicating the severity of COVID infection, such as the extent of oxygen requirements or admission to higher monitoring settings. In NSQIP, “a patient who is prescribed supplemental oxygen and utilizes it on a regular basis would be assigned as dyspnea upon moderate exertion unless there is documentation of dyspnea at rest”.

Statistical Analysis

1. Preprocessing
 1. Convert age from the NSQIP character variable to continuous variable, with Age “90+” recoded as 90
 2. Standardizing the coding of missing values: missing coded in NSQIP as “-99”, “unknown”, “None Assigned”, or “NULL”. Each variable will be individually examined to ensure that the missing value is correctly standardized.
 3. Missing values
 - Patients with missing data on key variables will be excluded as described in the inclusion/exclusion criteria.
 - For confounders in modeling, if
 1. >10% missing then exclude the confounder from the model
 2. <1% missing then delete case (complete case analysis)
 3. >=1% and <10% missing then multiple imputation

- The % of missing data for height and weight will be examined in cohort characteristics. If <1% is missing, then BMI will be calculated using these variables.

4. Check for collinearity with variance inflation factor and correlation matrix: if present, combine information from collinear variables if feasible (e.g. new variables is “yes” if “yes” in any of the variables); if not, eliminate the variable that has more missing values or would be less accurately ascertained
2. Descriptive statistics
 1. Cohort characteristics (perioperative and morbidity/mortality outcomes), including by 1) COVID-positive patients by SA vs. GA, 2) COVID-negative patients January-December 2021 vs. 2017-2019, 3) COVID-positive vs. negative in January-December 2021 stratified by anesthesia technique, and 4) utilization of SA vs. GA in 2021 (January-December) vs 2017-2019. Continuous variables will be presented as mean (standard deviation) and median (IQR) for parametric and nonparametric data, respectively. Categorical variables will be presented as frequency (%). For comparison amongst groups, ANOVA will be used for parametric data, Kruskal-Wallis for nonparametric data, and Chi-square for categorical data. Standardized mean difference will be presented.
3. Multivariable logistic regression
 1. To assess the association amongst anesthesia type and mortality in COVID-positive patients, a multivariable logistic regression will be performed using a priori exposure (SA vs. GA) and confounder variables (above) for the primary outcome of mortality. The same independent variables will be used in the multivariable logistic regressions for secondary outcomes (linear regression with log transformation for the outcome of length of stay).
4. Sensitivity and exploratory analysis include
 1. We will define the COVID-positive cohort using the additional definitions discussed above per Table 1.
 2. Cohort characteristics of the GA + SA group will be presented, and compared to the SA and GA groups. If this group consists of >1% of the respective cohort, the multivariable logistic regression for mortality will be repeated with GA+SA included as part of the GA group for the multivariable logistic regression.
 3. Repeat the primary modeling with the cohort after excluding patients with age “90” (all patients aged 90 and above are coded as 90+ in NSQIP, thus potential residual confounding)
 4. If there is sufficient sample size, subgroup analysis by sex (male only, female only) and age (<65, >=65 year old) may be performed.
 5. The degree of unmeasured confounding will be assessed using E-value and the Durbin-Wu-Hausman test.
 6. Adjustment for multiple testing for secondary outcomes, including Bonferroni, False Discovery Rate, and Holm's method
5. Sample size calculation
 1. There are approximately 10,000 patients in the NSQIP Hip fracture dataset per year. The prevalence of COVID-19 in the hip fracture patient population was 10% (thus an estimated sample size of approximately 1000 patients) (<https://www.ncbi.nlm.nih.gov/pmc/articles/PMC7495188>), with a mortality

of 36% in this population. The pre-pandemic SA:GA utilization ratio was approximately 1:4 (20). With 80% power and 0.05 alpha, the sample size required to detect a 10% absolute decrease in mortality rate with the SA exposure (from 36% to 26%) is 1064, and 525 for 14% absolute decrease in mortality rate, as calculated by the Sample Size Calculator (<https://clinicalcalc.com/stats/samplesize.aspx>).

2. For population cohort studies where logistic regression is used, the sample size recommended is at least 500 patients, or $100 + 50i$ (i =number of independent variables in the final model) (26). With an estimated sample size of 1000 patients, 18 independent variables can be included.
3. Sample size calculated based on R-squared (variance explained by the multi-variable logistic regression) and mortality difference between SA vs. GA (Table 2). Assumptions are: alpha = 0.05, baseline mortality rate 36%, ratio of SA:GA of 1:4. For example, with approximately 500-1000 patients from NSQIP, the study would likely be able to detect a 12 to 14% mortality difference depending on the R-squared.

Table 2. Sample size calculation for logistic regression using G*Power software.

Amount of R ² accounted for by covariates	Detectable difference in mortality			
	8%	10%	12%	14%
0.1	1820	1139	771	552
0.2	2048	1281	868	621
0.3	2340	1464	992	709
0.4	2730	1708	1157	827

1.

Data will be analyzed using R. Significance level will be set at P <0.05.

List of variables in cohort characteristics include but are not limited to (Please see Appendix 1 for details)

Patient characteristics: Age, sex, race, body mass index (BMI) (calculated from height and weight in NSQIP), American Society of Anesthesiologists (ASA) Physical Status (PS), smoker within one year preoperatively, severe obstructive chronic pulmonary disease (COPD), dyspnea, coagulopathy, congestive heart failure (CHF), hypertension on medications, preoperative renal failure (acute renal failure, dialysis, and/or GFR < 60 mL/min/1.73 m² based on preoperative creatinine) (25), diabetes, ascites, preoperative functional status, preoperative dementia/delirium, systemic sepsis, preoperative use of mobility aid, and preoperative pressure sore.

Surgical factors: Total operating time, year of surgery, hip fracture type, pathological fracture, and days from hospital admission to operation.

Systems factors: Medical co-management, and participation in a standardized hip fracture care program.

Postoperative variables:

- Mortality
- Myocardial infarction
- Stroke/CVA
- Postoperative delirium
- VTE (composite: pulmonary embolism, DVT)
- Pneumonia
- On ventilator >48h postoperatively
- Acute renal failure
- Sepsis or septic shock (composite of systemic sepsis and septic shock)
- Transfusion (packed red blood cell (PRBC) within the first 72 hours of surgery start time)
- Readmission: also present % unplanned
- Unplanned reoperation
- Still in Hospital > 30 Days
- Non-home discharge
- Weight bearing as tolerated (WBAT) on postoperative day (POD) #1
- Wound issues (composite: superficial and deep infection, wound disruption)
- New postoperative pressure sore
- Urinary tract infection

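### The 2021 COVID-negative cohort is partly defined by what happens after surgery, so its mortality is probably below that of all patients negative at surgery; only the descriptive comparisons are affected

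*Combined protocol and SAP*

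**What the plan says.** The COVID-19 cohorts section of the combined protocol and SAP states that "COVID-negative patients will be defined as rows 1 in Table 1, and COVID-positive patients will be defined as row 4". In Table 1, row 1 is No before and No after surgery; row 4 is laboratory confirmed before surgery and No after it. The same section explains the timing, "In NSQIP, preoperative COVID status denotes within 14 days before surgery", and adds that "patients with preoperative COVID are always coded “No” for postoperative COVID".

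Rows 2 and 3 are patients with a preoperative No who were confirmed (row 2) or suspected (row 3) afterwards. They are in neither primary cohort. The plan finds such patients hard to interpret, because of the incubation period and "the possibility of COVID-19 contraction while in hospital post-operatively". Its response is "we will perform sensitivity analysis using alternative definitions for the COVID-positive cohort": three variants, each changing who counts as positive.

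The cohort of patients without COVID serves two aims set out before the Methods and repeated under Descriptive statistics: outcomes without COVID in 2021 against 2017-2019, and outcomes with against without COVID in 2021, stratified by SA and GA.

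**The concern.** Membership of row 1 is settled only during follow-up, in the same period in which outcomes are counted: "The primary outcome is all-cause 30-day mortality following hip fracture surgery". A patient who was negative at surgery, caught COVID on the ward and died of it leaves the negative cohort, and the death leaves with the patient. Nothing comparable happens to row 4 or to the 2017-2019 cohort.

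Two descriptive results could be distorted. The contrast between patients with and without COVID could be overstated. Separately, 2021 mortality and morbidity without COVID could look favourable beside a pre-pandemic cohort from which nobody was removed for a postoperative event. Morbidity may be touched as well as mortality: a longer stay gives more time to be infected and tested, so row 1 may lose long-stay patients. That last step is an inference, not something the documents show.

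**Working it through.** **Is the asymmetry real?** Row 1 carries a postoperative condition. Row 4 also shows a postoperative No, but the plan says this is automatic coding, so it restricts nothing. (Row 6 pairs a suspected preoperative status with a confirmed postoperative one, so the coding rule can hold literally only for laboratory-confirmed preoperative cases; that is all row 4 needs.) The three sensitivity definitions use rows 2, 4 and 6; rows 4 and 6; and rows 2 to 6. None describes a negative cohort of rows 1 to 3. The first and third move postoperative cases into the positive cohort, so that cohort then depends on follow-up too. The Limitations section mentions COVID misclassification but not this selection.

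**The plan's own figures.** No figure in the plan depends on the negative definition. Its sample sizes concern SA against GA among COVID-positive patients. They reproduce with a two-sided comparison of two proportions, SA:GA 1:4, 80% power and alpha 0.05: 213 + 852 = 1065 against the stated 1064, and 106 + 424 = 530 against 525. They are unaffected.

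**Inputs for the size.**
- From the introduction: "35% in COVID-positive patients, vs. 2% in patients without COVID". I take 2% as row 1 mortality and 35% as row 4 mortality. The documents do not say that the 2% corresponds to row 1, so this is an assumption.
- Assumed: the share *f* of preoperatively negative patients who fall in rows 2 and 3, 1% to 5%.
- Assumed: 30-day mortality *m* in rows 2 and 3, 20% to 35%.

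**Formula.** Mortality in all preoperatively negative patients = (1 − *f*) × 2% + *f* × *m*. For example, 0.95 × 2% + 0.05 × 35% = 1.90% + 1.75% = 3.65%.

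| *f* | *m* | All preoperatively negative | Ratio, 35% to this | Risk difference (points) |
|---|---|---|---|---|
| row 1 only | – | 2.00% | 17.5 | 33.0 |
| 1% | 20% | 2.18% | 16.1 | 32.8 |
| 1% | 35% | 2.33% | 15.0 | 32.7 |
| 5% | 20% | 2.90% | 12.1 | 32.1 |
| 5% | 35% | 3.65% | 9.6 | 31.4 |

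If rows 2 and 3 died at 2%, nothing would move. At 1% mortality and *f* = 5% the shift reverses slightly: 0.95 × 2% + 0.05 × 1% = 1.95%.

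In the comparison with 2017-2019, the 2021 figure moves by 0.18 points (2.18 − 2.00) to 1.65 points (3.65 − 2.00). The documents give no 2017-2019 mortality to set this against.

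**Early deaths.** A patient who dies soon after surgery has little chance of a COVID diagnosis and stays in row 1. This raises row 1 mortality and lowers that of rows 2 and 3. A simulation with constant daily hazards over 30 days, 2% mortality without COVID and about 5% postoperative COVID gave:

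| Assumed hazard ratio of death after COVID | Row 1 | All preoperatively negative |
|---|---|---|
| 1 | 2.06% | 2.00% |
| 2 | 2.05% | 2.05% |
| 5 | 2.04% | 2.19% |
| 10 | 2.05% | 2.42% |
| 20 | 2.06% | 2.84% |

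The two effects balance at a hazard ratio of about 2. Above that, row 1 is the lower figure. Throughout, row 1 stays close to, and slightly above, the 2% set for patients without COVID.

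**The case against.** The strongest reply is about the target. The plan asks about patients without COVID infection, not patients negative at surgery, and row 1 is a natural way to express that. Against a never-infected population, the simulation finds row 1 nearly unbiased. Leaving ambiguous cases out of both primary cohorts is also deliberate and reasoned: rows 2 and 3 may contain infections already incubating at surgery, and nothing in the documents says how many. Both arguments stand. They are reasons to keep row 1, but not reasons to show it alone, because the plan never says which of the two populations it means.

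The 2021 against 2017-2019 aim deserves separate treatment. A reader might infer that both aims overstate a COVID contrast. This one contains no COVID contrast; its risk is a flattering 2021 figure. Adding rows 2 and 3 has its own drawback, since it puts COVID-related deaths on one side only.

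Finally, the size rests on assumptions and depends on the scale. The ratio can fall by almost half while the risk difference moves by less than 2 points. That is fair, and both scales should be given.

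**Conclusion.** The point holds in a limited form. Row 1 is filtered on an event during follow-up, while row 4 and the 2017-2019 cohort are not. Relative to all patients negative at surgery, row 1 mortality is probably too low, provided postoperative COVID raises the hazard of death to more than about double. The 35% against 2% that the plan cites makes this plausible but does not establish it. The illustrative range is 2.2% to 3.7% in place of 2%, before allowing for early deaths, and it rests wholly on the assumed share and mortality of rows 2 and 3.

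Three stronger readings are not supported. One is that row 1 mortality is biased low outright; that depends on the target population. Another is that the plan's own figures show high mortality in rows 2 and 3; the cited 35% is for COVID-positive patients generally, and the documents give neither counts nor deaths for those rows. The third is that the main result is compromised; the primary and secondary SA-against-GA analyses are run within COVID-positive patients and never use this cohort.

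**What to change.** For the two descriptive comparisons that use the 2021 COVID-negative cohort, keep row 1 and prespecify a sensitivity definition fixed at surgery: preoperative COVID No, rows 1 to 3. Report counts and deaths for rows 2 and 3 separately. Label each version by the question it answers: row 1 for patients with no recorded COVID before or after surgery, and rows 1 to 3 for patients negative at surgery, whatever happened afterwards. Give the with-versus-without contrast as a risk difference as well as a ratio.

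The cost is an extra column in planned tables and a short table for rows 2 and 3, using fields already coded; the primary model does not change. The drawbacks are that rows 2 and 3 may include infections incubating at surgery, and that against 2017-2019 they add COVID-related deaths to 2021 alone. Hence both definitions should be shown and neither should replace the other.

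### The 2021 COVID-negative cohort omits patients coded preoperatively as suspected COVID while 2017-2019 keeps their counterparts, so the descriptive period comparison is not like for like

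*Combined protocol and SAP*

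**What the plan says.** Methods, COVID-19 cohorts, sets the primary definitions: "COVID-negative patients will be defined as rows 1 in Table 1, and COVID-positive patients will be defined as row 4". Table 1 has two rows with a preoperative entry of suspected: row 5 (no postoperative COVID) and row 6 (laboratory confirmed postoperatively). The footnote, attached to row 5, reads: "Suspected denotes COVID-19 infection suspected by patient preoperative pneumonia or dyspnea".

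The comparator is the third cohort, "3) pre-pandemic from January 2017 to December 2019", with no row-type restriction. The exclusion criteria for all years do not mention pneumonia or dyspnea. COVID status enters the study only in 2021; the Setting section says "We will omit the data from January 2020 to December 2020 given there was no reporting of COVID status during this period".

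The objectives introduce the period comparison with "To provide context for interpretation, we will describe the epidemiology of the following rates during versus before the 2020 COVID-19 pandemic". The rates include mortality and morbidity of patients without COVID. Statistical Analysis, item 2 (Descriptive statistics), lists it as "COVID-negative patients January-December 2021 vs. 2017-2019" and adds: "For comparison amongst groups, ANOVA will be used for parametric data, Kruskal-Wallis for nonparametric data, and Chi-square for categorical data". The only regression concerns anesthetic technique among COVID-positive patients: "To assess the association amongst anesthesia type and mortality in COVID-positive patients, a multivariable logistic regression will be performed".

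**The concern.** A comparison of two periods should select patients by the same rule in each. Here 2021 patients must pass a preoperative test of not being suspected of COVID, and 2017-2019 patients face no such test. If suspicion was triggered by pneumonia or dyspnea in patients who did not have COVID, the 2021 group loses some patients with preoperative respiratory problems whose counterparts stay in the earlier group. Should those patients die more often, the 2021 rate falls with no change in outcome, or a real worsening during the pandemic is partly hidden. Morbidity outcomes such as pneumonia and prolonged ventilation could be affected in the same way.

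The row 1 group is also the without-COVID reference in the 2021 contrast of patients with and without infection, so it would look somewhat healthier there too. Both comparisons are meant to help readers interpret the main result, and both carry significance tests.

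**Working it through.** **Does the asymmetry follow from the text?**

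1. Row 1 requires no preoperative and no postoperative COVID. Rows 5 and 6 fail the first condition, so they are not COVID-negative. They are not row 4, so they are not COVID-positive either.
2. The 2017-2019 cohort takes all eligible patients, including any who would have been suspected had the code existed.
3. Nothing later restores the balance. The three alternative definitions (rows 2, 4 and 6; rows 4 and 6; rows 2 to 6) change the COVID-positive cohort only. The period comparison is unadjusted. Preoperative pneumonia is in neither the confounder list nor the listed patient characteristics, although the latter is stated not to be exhaustive. The Limitations section mentions COVID misclassification in general, not a filter applied to one period.

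**Who causes bias?** Only suspected patients who did not have COVID. Leaving out true cases is right for a cohort without infection. That covers row 6, which is laboratory confirmed, and an unknown part of row 5.

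**How large could it be?** The plan gives no figure for this comparison, so there is none to reproduce. The following is an illustration.

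Inputs from the documents (Sample size calculation): about 10,000 patients per year, hence 30,000 for 2017-2019; 10% COVID prevalence, hence about 9,000 without COVID in 2021; significance at P<0.05, taken as two-sided.

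Assumed inputs: true mortality m = 5% in both periods; d = share of 2021 patients without COVID who are removed as suspected; r = their mortality relative to row 1, taken as 2 to 3.

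Formulas:
- Row 1 mortality: p = m / [(1 − d) + d·r]
- Apparent fall: D = m − p
- SE = √[m(1 − m)/30,000 + p(1 − p)/(9,000(1 − d))]
- Chance of P<0.05 = Φ(D/SE − 1.96) + Φ(−D/SE − 1.96)

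Example, d = 5% and r = 3: p = 0.05/(0.95 + 0.15) = 4.55%; D = 0.455 points; 2021 n = 8,550; SE = 0.258 points; D/SE = 1.76; chance 42%.

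| d | r | Row 1 mortality | Apparent fall (points) | Chance of P<0.05 |
|---|---|---|---|---|
| 0.25% | 2 | 4.99% | 0.01 | 5.0% |
| 1% | 2 | 4.95% | 0.05 | 5.4% |
| 1% | 3 | 4.90% | 0.10 | 6.6% |
| 5% | 2 | 4.76% | 0.24 | 15% |
| 5% | 3 | 4.55% | 0.45 | 42% |
| 10% | 2 | 4.55% | 0.45 | 41% |
| 10% | 3 | 4.17% | 0.83 | 90% |

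With no true change the chance should be 5%. If r = 1 there is no artefact at any d. At the 2% mortality that the background gives for patients without COVID, the chance is 5.0-5.6% for d of 0.25-1% and 9-53% for d of 5-10%.

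The patient numbers ignore the exclusions for platelets, coagulation, ASA V and technique. If 30% were excluded (assumed), the 90% becomes 78% and the 53% becomes 40%.

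**The case against.** A reader might infer that 2021 loses everyone with preoperative pneumonia or dyspnea. The documents do not support that. Table 1 is an NSQIP classification and its entry is a recorded suspicion of COVID; the footnote says what suspicion rested on. A 2021 patient with either condition but no recorded suspicion stays in row 1. The upper end of the table is reached only if the code is frequent, and nothing in the documents shows that it is.

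A reader might also infer that the period comparison is bound to favor 2021. That does not follow either. The plan itself notes that NSQIP has no COVID history earlier than 14 days before surgery and that recent infection raises mortality. Such patients sit in row 1 and push 2021 mortality up. The selection described here has a known direction under its stated conditions; the net bias does not.

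Third, the comparison is context, listed under descriptive statistics. At 2% mortality the largest fall considered is 0.33 points, small beside the background's gap between 35% and 2% (33 points).

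All three points stand, and they limit the size and importance of the concern. They do not remove the one-sided rule. The plan tests the period comparison at P<0.05, has no analysis that would reveal the effect, and does not commit to reporting how many patients are in rows 5 and 6.

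**Conclusion.** The concern holds in a limited form. The 2021 COVID-negative cohort is selected on a preoperative suspicion code that could not exist in 2017-2019. This lowers 2021 COVID-negative mortality and morbidity to the extent that row 5 patients did not have COVID and had worse outcomes; that they did is a reasonable inference, not a statement in the documents.

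The size is unknown. On the assumptions above it is negligible at a share of 1% or less and material only at about 5-10%. Because d counts only suspected patients without COVID, the coded share would have to be larger still where some of them were infected.

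The primary and secondary SA versus GA analyses use row 4 only and are not affected. The effect is confined to the period comparison and, less importantly, the reference group for the with-versus-without-COVID contrast. It is worth correcting because the correction is cheap and is best specified before the data are seen.

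**What to change.** 1. Keep row 1 against 2017-2019 as planned.
2. Add a pre-specified sensitivity tabulation of 2021 rows 1 plus 5 (no laboratory-confirmed COVID and not suspected postoperatively) against 2017-2019.
3. Report the number of patients and their mortality in each of rows 1-6.
4. Read the period comparison from both versions, and add a sentence to Limitations on the one-sided code.
5. While editing, reconcile the statement that patients with preoperative COVID are always coded negative postoperatively with row 6, which shows a preoperative suspected entry and a postoperative confirmed one.

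The cost is some SAP wording and one more tabulation from the classification already needed for Table 1. The small downside is that adding row 5 brings in some true COVID cases, so neither version is definitive alone.

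A version restricted in both periods to patients without preoperative pneumonia or dyspnea is optional. It describes a different population, is not a bound on the planned comparison, and depends on the pneumonia field being extracted.
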